#### Revision History:

Revision	Description	Date
1.0	Initial Release of Clinical Study Plan	20APR2020
2.0	Amendment of the Clinical Study Plan Addition of 6-month visit	02FEB2021
3.0	Amendment of the Clinical Study Plan Addition of 12-month visit	30JUL2021

## PROTOCOL SYNOPSIS

Study Title	A Post-Market, Observational Clinical Study to Evaluate the Effects of DTM™ SCS programming in treating Intractable Chronic Upper Limb Pain
Protocol Number	DTM-PROC-2020PM3
Study Device	Intellis™ neurostimulator, a Spinal Cord Stimulation (SCS) device system manufactured and commercialized by Medtronic (Minneapolis, MN)
Study Purpose	The purpose of this observational clinical study is to evaluate the effectiveness and to collect safety data of DTM™ SCS programming on subjects with chronic, unilateral or bilateral upper limb pain.
Study Design	This is a post-market, open-label, prospective, multi-center, observational study evaluating upper limb pain relief with the DTM SCS programming approach. Data at follow-up visits will be compared to baseline assessments collected at the beginning of the study.
Study Size	Up to 90 subjects may be consented and screened in clinical sites in the United States. This would allow approximately 45 subjects to be implanted.
Study Duration	The expected total duration of this study is approximately 26months. Enrollment of subjects is expected to last 20 months. Subjects that have received the permanent implant will be followed up for 12 months after their device has been activated. A subject will likely be committed to the study for about 14 months. This consists of Baseline assessments, up to 10 days of trial stimulation and 12months of treatment following implantation and activation of the device. All current subjects or those who have completed their 6-month visit will be offered to return for an additional 12-month visit. This would increase their commitment to the study to 14 months.
Study Objective	The primary objective of this study is to evaluate the effectiveness of DTM SCS programming as a treatment for reducing intractable chronic pain of the upper limbs.

	
The secondary objectives of this study are to further characterize the effectiveness of DTM SCS programming for the treatment of chronic pain of the upper limb and to collect safety data of DTM SCS programming.

Inclusion Criteria	
A subject must MEET ALL of the following inclusion criteria:
 
 
1. Be diagnosed with chronic, intractable pain of the upper limb related to the cervical spine and/or neuropathic arm pain.
 
2. Be a candidate for SCS system (trial and implant) per labeled indication (upper limb pain due to one of the conditions listed in indications statement)
 
3. Considering daily activity and rest, has average upper limb pain intensity of <math>\geq 5</math> out of 10 cm on the Visual Analog Scale (VAS) at enrollment
 
4. Be willing and capable of giving written informed consent to participate in this clinical study based on voluntary agreement after a thorough explanation of the subject's participation has been provided.
 
5. Be willing and capable of subjective evaluation, read and understand written questionnaires, and read, understand and sign the written informed consent.
 
6. Be 18 years of age or older at the time of enrollment
 
7. Be on a stable pain medication regime, as determined by the study Investigator, for at least 30 days prior to enrolling in this study
 
8. Be willing and able to comply with study-related requirements, procedures, and visits, including not increasing pain medications through the three month visit
 
9. Has adequate cognitive ability to use a patient programmer and recharger as determined by the Investigator
 

Exclusion Criteria	
A subject must NOT MEET ANY of the following exclusion criteria:
 
 
1. Has a medical, anatomical, and/or psychosocial condition that is contraindicated for commercially available Intellis™ SCS systems as determined by the Investigator
 
2. Have a medical condition or pain in other area(s), not intended to be treated with SCS, that could interfere with study procedures, as determined by the Investigator
 
3. Currently enrolled or planning to enroll in an interventional clinical study that could potentially confound the study results (co-enrollment in an interventional study is only allowed when documented pre-approval is obtained from the study manager or designee)
 
4. Has an existing active implanted device such as a pacemaker, another SCS unit, peripheral nerve stimulator, and/or drug delivery pump.
 
5. Has pain in other area(s) and/or medical condition requiring the regular use of significant pain medications that could interfere with accurate pain
 

	
reporting, study procedures, and/or confound evaluation of study endpoints, as determined by the Investigator
 
 
6. Has significant cervical stenosis, as determined by the Investigator
 
7. Has facet spondylosis, as determined by the Investigator
 
8. Has mechanical spine instability, as determined by the Investigator
 
9. Has undergone, within 30 days prior to enrollment, an interventional procedure and/or surgery to treat upper limb pain, which is providing significant pain relief
 
10. Has unresolved major issues of secondary gain (e.g., social, financial, legal, such as worker compensation matters)
 
11. Be pregnant as determined by urine testing unless female subject is surgically sterile or post-menopausal. If female, sexually active, and childbearing age, subject must be willing to use a reliable form of birth control.
 
12. Have evidence of an active disruptive psychological or psychiatric disorder as determined by a psychologist
 
13. Have a current diagnosis of a progressive neurological disease as determined by the Investigator
 
14. Have a current diagnosis of a coagulation disorder, bleeding diathesis, progressive peripheral vascular disease or uncontrolled diabetes mellitus
 
15. Have a condition that the Investigator determines would significantly increase perioperative risk
 
16. Any previous history of surgery on the posterior elements (laminectomy, posterior fusion) of the cervical spine
 
17. Have metastatic malignant disease or active local malignant disease
 
18. Have a life expectancy of less than 1 year
 
19. Have an active systemic or local infection
 
20. Have within 6 months of enrollment a significant untreated addiction to dependency producing medications or have been a substance abuser (including alcohol and illicit drugs)
 

Primary Endpoint	The primary efficacy endpoint is the percentage of implanted subjects who respond to DTM SCS therapy at 3-months after device activation. An individual responder is a subject that experiences at least a 50% decrease in upper limb pain relative to baseline assessment.

## **A. PURPOSE**

### **A.1. STUDY DEVICE**

The Intellis™ neurostimulator is a commercially available implantable component of a Spinal Cord Stimulation (SCS) device system manufactured by Medtronic (Minneapolis, MN). The system is indicated for spinal cord stimulation (SCS) as an aid in the management of chronic intractable pain of the trunk and/or limbs. It is designed to deliver electrical stimulation to the spinal cord using arrays of electrodes (also called leads) placed in the dorsal epidural space. The study will use the commercially available Intellis™ neurostimulator and compatible SCS system components from Medtronic using stimulation parameters within the specifications approved for use in the approved indications. The study will stimulate the cervical dorsal columns of the spinal cord. Section D of this Clinical Study Plan provides detailed description of Intellis™ neurostimulator.

### **A.2. PURPOSE OF THE INVESTIGATION**

The purpose of this post-market, observation study is to characterize the effectiveness and collect safety data of DTM SCS programming on subjects with chronic, intractable unilateral or bilateral pain of the upper limbs. This study is an observational, open-label, multi-center, prospective evaluation of treatment outcomes resulting from the DTM SCS programming approach relative to pretreatment measurements. The DTM SCS programming approach will be discussed in section B.1 of this Clinical Study Plan.

This investigation will utilize a commercially available SCS system (Intellis™ neurostimulator and compatible SCS components) as is, without any modification, and using FDA-approved parameters. Outcomes will be assessed via standardized tests.

### **A.3. STUDY SIZE**

Approximately 45 subjects are expected to complete the 3-month endpoint of the study. Up to 90 subjects may be consented to participate at clinical sites in the United States. A sample size estimate is discussed further in section B.5.5 of this Clinical Study Plan.

#### **A.4. DURATION OF THE INVESTIGATION**

The expected total duration of this study is approximately 26 months. Enrollment of subjects is expected to last 20 months. Subjects that have received the permanent implant will be followed up for 12 months after their device has been activated. A subject will likely be committed to the study for about 14 months. This consists of Baseline assessments, up to 10 days of trial stimulation, and 12 months of treatment following implantation and activation of the device. All current subjects or those who have completed their 6-month visit will be offered to return for an additional 12-month visit. This would increase their commitment to the study to 14 months.

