#### **B.6.1. SUMMARY OF STUDY PROTOCOL**

Potential study subjects will be identified from a pool of candidates for SCS therapy that are either affiliated with or referred to the clinical sites. Advertisements of the study may be used for recruitment purposes, upon approval of the patient recruitment materials by the study IRB(s). An informed consent form (ICF) will be given to the potential subject for private evaluation. The Investigator or Study Clinical Staff will be available to respond to

any questions the potential subject may have during evaluation of the ICF. Potential study subjects willing to participate in the study will visit the study site for providing written consent and for evaluation of eligibility to participate based on inclusion and exclusion criteria. Once a consented subject is deemed qualified to participate in the study, baseline assessments will occur followed by scheduling of the trial stimulation phase.

Subjects who complete a successful DTM SCS trial phase will be scheduled to receive a permanent implant of the SCS system and will undergo 3 months of therapy with assessments at 1, 3, 6 and 12 months after the activation of the implanted device. All current subjects or those who have completed their 6-month visit will be offered to return for an additional 12-month visit. This would increase their commitment to the study to 14 months. Baseline assessments will include measures for pain intensity, use of medication, and extent of disability.

Subjects will undergo a Trial Phase lasting up to 10 days to determine subject's response to DTM SCS. Commercially available stimulation leads and a commercially available external neurostimulator (ENS) will be used during the Trial Phase. Subjects will evaluate DTM SCS therapy based on pain intensity under optimal stimulation parameters within the specifications of the device. Subjects who have a "successful Trial Phase" (defined as a 40% or greater pain reduction from Baseline in their upper limb pain) will proceed to permanent implantation of a SCS system.

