### **B.6.2. PRE-SCREENING/CONSENT/ENROLLMENT**

[figure not shown]
Medical records of all subjects deemed by the Investigator to be potential candidates for the study will be de-identified and sent to a sponsor designated physician for pre-screening. De-identified medical records should include detailed medical and surgical history of the pain condition under study as well any information about comorbidities. Any imaging studies (such as MRI, CT, X-ray) should be included for evaluation of the study candidate. Once the site has received confirmation that subject may be an appropriate candidate for this study, the site may proceed with the eligibility process. This de-identified pre-screening process assists in reducing unnecessary visits for subjects that would not be eligible for this study.

Written informed consent for participation in the study must be obtained from subjects

before initiation of any study-related activities, including those that assess eligibility. Following informed consent, subjects will be assigned a unique subject identification number and will be considered to be enrolled in the study. Eligibility for advancing to the next stage of the study will be evaluated by the site Investigator based on the defined inclusion and exclusion criteria. Subjects will be assessed for pain intensity and disability.

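### B.7.1 analyses only implanted subjects who finish the study, while the primary endpoint in B.7.3 counts implanted subjects at 3 months; the 26-month duration and the completion text also need reconciling

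*Combined protocol and SAP*

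**What the plan says.** **Population and endpoint.** B.7.1 defines one analysis population: subjects with a permanent implant who finish the study and have no major deviation that makes their data unusable. It names no visit. B.7.2 places the primary effectiveness assessment, for subjects with a successful trial and an implant, at the 3-month visit. B.7.3 takes implanted subjects as the base of the responder percentage at 3 months. A.3 expects about 45 subjects to reach the 3-month endpoint; the Synopsis and B.5.4.1 give the same number as implanted.

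**Duration.** A.4 states "The expected total duration of this study is approximately 26 months. Enrollment of subjects is expected to last 20 months". The Synopsis and B.5.5 give the same two figures. A.4 adds "Subjects that have received the permanent implant will be followed up for 12 months after their device has been activated" and "A subject will likely be committed to the study for about 14 months". It then says of the additional 12-month visit: "This would increase their commitment to the study to 14 months". B.6.2 starts enrollment at consent: "Following informed consent, subjects will be assigned a unique subject identification number and will be considered to be enrolled in the study".

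**Completion.** B.6.12 and B.6.19 end participation at the 3-month visit, and B.6.19 then offers only a 6-month visit. B.6.13 calls the 12-month visit additional and B.6.14 calls it optional. B.6.18 expects everyone to attend through 12 months, then offers the 12-month visit as an extra. B.6.1 says that subjects "will undergo 3 months of therapy with assessments at 1, 3, 6 and 12 months after the activation of the implanted device". In Table 1 the Study Completion row has a firm mark at 12 months and optional marks at 3 and 6 months. Note c explains that some subjects consented only to the shorter follow-up.

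**Adverse events.** B.7.4 lists the frequency of treatment-emergent events with no time point. B.8.3.2 captures events until the study is completed. B.6.1 and Table 1 schedule assessment through 12 months.

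**The concern.** With no hypothesis test, the responder percentage is the whole primary result, so its denominator should be fixed before the data are seen. B.7.1 and B.7.3 give different denominators. The subjects on whom they differ are not a random subset: B.6.16 and B.6.17 name explant, adverse events and unsatisfactory effectiveness among the routes out. If such subjects respond less often than the rest (an assumption; the documents give no data), leaving them out raises the reported percentage. The conflicting completion text makes this worse, because it decides whether withdrawals after month 3 also count against inclusion.

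The duration figures, the completion wording and the missing adverse event window are smaller matters. They affect planning and how the safety table is read, not the 3-month measurements.

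**Working it through.** **1. Who is counted.** The table applies each definition to an implanted subject.

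| Implanted subject | B.7.3 | B.7.1, completion at 3 months | B.7.1, completion at 12 months |
|---|---|---|---|
| Attends every visit | in | in | in |
| Has a 3-month VAS, declines the later visit | in | in | probably in (B.6.18, Table 1 note c) |
| Has a 3-month VAS, then withdraws or is explanted | in | in | out |
| Withdraws or is explanted before month 3 | in, no 3-month result | out | out |
| Has a 3-month VAS and a disqualifying deviation | in | out | out |

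The definitions differ in both B.7.1 columns, so choosing a completion date does not by itself remove the mismatch. The 12-month reading adds the third row.

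**2. Size.** One subject of 45 is 1/45 = 2.2% of the planned denominator. The documents give no withdrawal rate, so the total effect cannot be estimated. For scale only, assume 27 of 45 respond (60.0%), and let the subjects left out be all responders or all non-responders:

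- Five left out: (27 − 5)/40 = 55.0% to 27/40 = 67.5%.
- Nine left out: (27 − 9)/36 = 50.0% to 27/36 = 75.0%.
- Five left out with 22 responders assumed: 17/40 = 42.5% to 22/40 = 55.0%. With 31: 26/40 = 65.0% to 31/40 = 77.5%.

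The responder counts and the numbers left out are assumptions, and the bands are extremes, not forecasts.

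**3. Duration.** Total = enrollment period + time in study of the last subject enrolled, with a month of 30.44 days. The longest stated lead-in is 10 + 60 + 14 = 84 days = 2.76 months (trial, wait for implant, wait for activation). Time from consent to trial start has no stated limit and is left out, so the long ends are not upper bounds. Visit windows are 31 days = 1.02 months (6 and 12 months) and 21 days = 0.69 months (3 months).

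The plan's figure of 26 is not reproduced with 12 months of follow-up:

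- Typical: 20 + 14 = 34.
- Shortest: 20 + 12 − 1.02 = 30.98.
- Longest stated: 20 + 2.76 + 12 + 1.02 = 35.78.

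The gap is 34 − 26 = 8 months (30.98 − 26 = 4.98 to 35.78 − 26 = 9.78).

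Shorter follow-up does contain 26:

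- 6 months: 20 + 6 − 1.02 = 24.98 to 20 + 2.76 + 6 + 1.02 = 29.78.
- 3 months: 20 + 3 − 0.69 = 22.31 to 20 + 2.76 + 3 + 0.69 = 26.45.

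If 26 and 12 months of follow-up both stand, enrollment must last about 26 − 14 = 12 months (26 − 15.78 = 10.22 to 26 − 10.98 = 15.02).

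**4. Adverse events.** B.6.1, B.8.3 and Table 1 together support assessment at every visit through 12 months. The B.7.4 endpoint does not say whether its frequency covers all of that period. Under staged consent, fewer subjects may contribute at 6 and 12 months than at 3.

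**The case against.** The best reply is that the plan can be read sensibly. B.7.2 fixes the primary assessment at 3 months, A.3 speaks of reaching the 3-month endpoint, and the deviation clause in B.7.1 is about usable data. All three favour keeping a subject who has a valid 3-month VAS. Table 1 with note c, and the route in B.6.18 for those who decline, give a partly workable completion rule; the 3-month wording in B.6.12 and B.6.19 may simply not have been updated. Adverse event assessment through 12 months is already stated. The study is descriptive, and no estimate depends on the 26 months.

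Most of this stands, and it limits the point. It does not change the words of B.7.1, which still require a subject to finish the study. Nor does the 3-month reading remove the loss of subjects who leave before month 3.

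A reader might go further in four ways that the documents do not support:

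- That completion has no definition at all. Table 1 and B.6.18 supply much of one. A.4 gives follow-up and commitment, not a completion point.
- That subjects who merely decline the extra visit are lost from the primary analysis. B.6.18 has a completion form filled in for subjects who do not stay on, and note c allows for them.
- That adverse event collection stops at 3 months. B.6.1, B.8.3 and Table 1 say otherwise.
- That 26 months is shown to be a leftover from a shorter plan. The revision history records "Amendment of the Clinical Study Plan Addition of 12-month visit", and 26 fits 3- or 6-month follow-up, but the cause is an inference.

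**Conclusion.** The main point holds: B.7.1 and B.7.3 define different denominators for the primary endpoint under any completion date, and the difference widens if completion means 12 months. Its size is unknown, because the documents give no withdrawal rate; each affected subject is 2.2% of the planned 45. The direction depends on whether the subjects left out responded. It should be settled before analysis.

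The rest is minor. The stated total is about 8 months short (5.0 to 9.8) if 20 months of enrollment and 12 months of follow-up both stand. A reader might infer that this gap bears on the results; it does not, since no estimate or visit is derived from it. The completion passages contradict one another and need reconciling. The adverse event endpoint lacks a time phrase. The 3-month measurements are not threatened, and no alpha, power or hypothesis test is involved.

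**What to change.** 1. In B.7.1, define the population for the primary endpoint as all implanted subjects, assessed at the 3-month visit, whether or not they later complete. Report how many have no 3-month VAS, so that a reader can recompute the percentage with them counted as non-responders.
2. In the Synopsis, A.4 and B.5.5, restate the total as about 34 months if both 20 months of enrollment and 12 months of follow-up stand; otherwise give the enrollment period that fits 26 (about 12 months). Correct the sentence that raises commitment from 14 months to 14 months.
3. Reconcile B.6.1, B.6.12, B.6.13, B.6.14, B.6.18 and B.6.19 with the Study Completion row and note c of Table 1, with separate wording for subjects consented under earlier versions.
4. In B.7.4, state the window for the adverse event frequency, consistent with B.6.1 and Table 1 (through 12 months), and report the number of subjects contributing at 6 and 12 months.

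The cost is text edits in eleven places (Synopsis, A.4, B.5.5, six parts of B.6, B.7.1 and B.7.4) and possibly a longer stated timeline. No visit or procedure is added. The edits do not remove self-selection into the 12-month visit.

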#### **B.1. RATIONALE FOR STUDY**

It is estimated that about 20% percent of the population worldwide is affected by moderate to severe chronic pain. Chronic pain becomes a burden to the individual as this affects a person's ability to carry out many daily life activities, such as exercising, walking, driving a car, attending social events, or performing household chores. In the United States, chronic pain is considered one of the most pervasive and intractable conditions affecting at least one third of the population at an estimated cost of five hundred billion dollars per year, when combining health-related expenditure and the cost-impact on loss of productivity and income. Low back pain, neck pain and limb pain are among the most prevalent pain conditions worldwide, all of them ranked in the top 10 for the most disabling conditions.

Conventional medical management, including medication and physical therapy, is often not adequate for treating chronic pain. Medication therapy based on opioids may also lead to addiction. Extensive use of opioid medications in the United States has led to the declaration of an epidemic crisis. Furthermore, surgical interventions have also failed to remediate severe cases of neuropathies and intractable pain for many patients. Spinal cord stimulation (SCS) is a proven therapy that has been in use for about 50 years for various types of chronic pain. It is currently indicated for the treatment of intractable chronic pain of the trunk and/or limbs. SCS is a reversible therapy that allows patients to evaluate the therapy for several days using an external neurostimulator (ENS) prior to receiving an implantable neurostimulator (INS) system. Spinal Cord Stimulation (SCS) utilizes pulsed electric fields that are applied to the dorsal section of the spinal cord via electrode arrays, called leads, implanted in the epidural space.

The conventional programming approach in SCS utilizes pulsed electric fields oscillating in the 40-250 Hz frequency range. The electric field induces a stimulation pattern (paresthesia), which is steered by the clinician and patient to overlay with the targeted pain location by modifying the duration (pulse width) and intensity of the applied electric field. The concept behind this programming approach is that the stimulation pattern induced by the electric field masks pain signals travelling to the brain. Although proven effective for the treatment of intractable chronic pain of the upper limbs by some practitioners, the variability of the paresthesia sensation, including uncomfortable sensations, due to the motion of the neck

have limited the utilization of the conventional SCS programming approach.

The DTM SCS programming approach relies on stimulation parameters that can be set by the clinician and patient to levels that avoid uncomfortable stimulation upon motion of the neck, while providing pain relief on the affected limb(s). DTM SCS programming will use stimulation parameters that are currently available in the device to be used in this study.

In a given therapy group, DTM SCS will provide programs with different pulse rates, pulse widths and intensities for the goal of better pain relief. For example, starting parameters may be a combination of a program with 50 Hz pulses with a duration of up to 200 microseconds and a program with 300 Hz pulsed with a pulse duration of up to 200 microseconds, while intensities will be custom adjusted by the patient for optimal pain relief and therapy comfort. It is anticipated that the low pulse amplitudes used in the DTM SCS programming approach would result in patients experiencing less uncomfortable stimulation events with the motion of the neck and upper limbs than what they might experience with a conventional SCS programming approach while providing effective pain relief. Should DTM SCS programming be shown to be effective and safe in this observational study, DTM SCS may offer an alternative approach that will help thousands of chronic pain sufferers make substantial improvement in pain relief, reduction in disabilities, and reduce the likelihood of uncomfortable paresthesia.

The study design is a post-market, open-label, prospective, observational multi-center study that will evaluate DTM SCS for chronic upper limb pain sufferers. Subjects participating in the study will trial SCS according to standard practice. Those who experience a successful trial will be eligible to get a permanently implanted device and evaluate the primary effectiveness point.

